2.2 STUDY OBJECTIVES

Primary objective - To Characterize the UC Patient Group Treated with Tofacitinib.

- a. Patient demographics at tofacitinib treatment initiation: age, gender, weight, height, smoking status, body mass index (BMI), treating hospital.
- b. Disease characteristics: age at diagnosis, duration of disease, and extent of colonic involvement according to the Montreal classification: E1 (ulcerative proctitis), E2 (left sided, distal colitis), E3 (pancolitis).
- c. Disease severity as assessed by Mayo score and f-calpro at the initiation of tofacitinib use.
- d. Laboratory results for biochemical inflammatory markers plasma C-reactive protein (P-CRP), blood thrombocytes (B-thromb), plasma albumin (P-alb), blood leukocytes (B-leuk), blood lymphocytes (B-ly), blood neutrophiles (B-neutr), blood hemoglobin (B-hb) and f-calpro at the start of tofacitinib treatment (baseline data).

e. Endoscopic findings including histology at the start of tofacitinib treatment (baseline data).

Secondary objective 1 - To Assess the Real-world Effectiveness of Tofacitinib.

- a. Proportion of patients who are taking to facitinib at week 8, 16, 24 and 52.
- b. To assess rates of clinical remission defined by a full or partial Mayo score at week 8, 16, 24 and 52.
- c. To assess rates of clinical response defined by a full or partial Mayo score at week 8, 16, 24 and 52.
 - note, objectives b and c were formulated as "rates" in the protocol, whereas the goal is to report "proportion of patients" as in majority of the other effectiveness objectives
- d. Proportion of patients in steroid-free clinical remission at weeks 8, 16, 24, and 52 as defined by full or partial Mayo who did not require any corticosteroid treatment during the period ≥4 weeks prior to the visit (for all patients and for those treated with corticosteroids at baseline).
- e. Proportion of patients reaching clinical response as defined by full or partial Mayo score at week 8, 16, 24 and 52.
 - note, objectives c and e were unintentional duplicates left in the protocol development
- f. Time to response as assessed by a decrease as defined by full or partial Mayo score.
- g. Proportion of responders defined by a f-calpro reduction of $\geq 50\%$, $\geq 75\%$ or $\geq 90\%$ at week 8, 16, 24 and 52 compared to baseline.

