- h. Proportion of patients reaching f-calpro below 250 mg/kg at week 8, 16, 24 and 52 of those that had f-calprotectin above 250 mg/kg at baseline and change from baseline in f-calpro at week 8, 16, 24 and 52.
- i. Proportion of patients in sustained remission (pMayo and full Mayo score) from week 8 to week 16, 24 and 52.
- j. Proportion of patients in sustained remission (pMayo and full Mayo score) from week 16 to week 24 and 52.

[figure not shown]
k. Proportion of patients in sustained steroid free remission (pMayo and full Mayo score) at week 16 to 24 and 52 (for all patients and for those treated with corticosteroids at baseline).

- *l.* Change in partial and full Mayo score at weeks 8/16/24/52.
- m. Proportion of patients in sustained endoscopic remission (sub score = 0), mucosal healing (sub score 0-1) or endoscopic response (sub score reduction from baseline of ≥ 1) from week 8 to week 16, 24 and 52.
- n. Proportion of patients in physician assessed histological remission determined as inactive disease, or normal histology, and change from baseline in histology assessment (0= normal histology, I= inactive disease and 2 = active disease) at week 8/16/24/52.
- o. Proportion of patients in sustained steroid free remission (pMayo and full Mayo score) (for all patients and for those treated with corticosteroids at baseline) and endoscopic remission (sub score = 0), mucosal healing (sub score 0-1) or endoscopic response (sub score reduction from baseline of ≥ 1) from week 8 to week 16, 24 and 52.
- p. Comparison of response and remission (pMayo and full Mayo score) based on the extent of colonic involvement.
- q. Proportion of patients with corticosteroid tapering at weeks 8/16/24/52 and their tapering rates and doses.
 - note after further discussions, the data required for objective q might not be present in the available medical records and/or prescriptions
- r. Proportion of patients with improvement in stool frequency sub score of 1 or more points and change from baseline in stool frequency sub score at week 8, 16, 24 and 52.
- s. Proportion of patients with improvement in rectal bleeding subscore of 1 or more points and change from baseline in rectal bleeding subscore at week 8, 16, 24 and 52.
- t. Proportion of patients reaching normal P-CRP levels (below 4mg/L) and change from baseline in P-CRP levels at week 8/16/24/52.

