7.2 STATISTICAL ANALYSES

Primary objectives a-e:

Describe the patient population at the baseline (initiation of tofacitinib), using the data collected. For each continuous variables (age, BMI, age at diagnosis, duration of disease, laboratory measures), provide the mean, median, sd, 25%Q and 75%Q values. For categorical variables (sex, smoking status, extent of colonic involvement, disease severity, endoscopic findings), report the number of patients, and proportion. Report proportion of missing values if present.

Secondary objective - Assess the Real-world Effectiveness of Tofacitinib

Secondary objective a:

For each patient, define the "on treatment" as Yes/No based on the latest available dose (at each timepoint 8, 16, 24 and 52 weeks). Patients marked with "not on treatment" prior to timepoint will be regarded as discontinued.

Report the proportion of patients on treatment, not censored at each timepoint.

Secondary objectives b, c, d, e, g, n:

For each patient, define the fulfilment of the remission/response criteria as Yes/No based on the latest available data (at each timepoint 8, 16, 24 and 52 weeks).

Report the proportion of patients on fulfilling the response/remission criteria, not censored at each timepoint.

Secondary objective f:

Define the time of response for each patient as first ever data-entry that fulfils response criteria. Fit competing-risk time-to-event model to the data, with time-to-event defined as time from index until response (event) or discontinuation (competing event), or end of data collection (censoring event).

Assess the cumulative incidence as function of time for both types of events. Illustrate the Aalen-Johansen state probabilities of multistate model.

Secondary objective h:

Select only patients with baseline f-calprotectin above 250 mg/kg at baseline. For each subsequent f-calprotectin measure, define below 250 mg/kg as Yes/No variable. Additionally, estimate the absolute delta change per baseline value.

For each timepoint (week 8, 16, 24 and 52), report the proportion of patients on fulfilling the <250mg/kg criteria, and summary statistics (mean, median, sd, 25%Q and 75%Q) of delta change, among patients not censored at each timepoint.

Secondary objectives i, j, k, m, o:

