Select only patients that were on remission/steroid free remission at the timepoints. For each patient, define the fulfilment of the remission/response criteria as Yes/No based on the latest available data (at each timepoint 16, 24 and 52 weeks). Report the proportion of patients on fulfilling the remission criteria, not censored at each timepoint.

Secondary objective l:

For each available Mayo score (full or partial), estimate the absolute delta change from baseline value. For each timepoint (week 8, 16, 24 and 52), report the summary statistics (mean, median, sd, 25%Q and 75%Q) of delta change, among patients not censored at each timepoint.

Secondary objective p:

Perform analyses described in secondary objective b and c, stratified by the extent of colonic involvement

Secondary objective q:

For each patient, define the corticosteroid tapering as Yes/No based on the latest available data (at each timepoint 8, 16, 24 and 52 weeks). Additionally, define the tapering rates and doses based on latest available data.

For each timepoint (week 8, 16, 24 and 52), report the proportion of patients that had corticosteroid tapered, among patients not censored at each timepoint. Additionally,

report summary statistics (mean, median, sd, 25%Q and 75%Q) of tapering rates and doses among patients that had corticosteroids tapered.

Secondary objectives r and s:

For each patient, define the fulfilment of the improvement criteria as Yes/No based on the latest available data (at each timepoint 8, 16, 24 and 52 weeks). Additionally, estimate the absolute delta change per baseline value

Report the proportion of patients on fulfilling the response/remission criteria, report the summary statistics (mean, median, sd, 25%Q and 75%Q) of delta change, among patients not censored at each timepoint.

Secondary objectives t-z:

For each subsequent laboratory measure, define "normal-level" as Yes/No variable. Additionally, estimate the absolute delta change per baseline value. For each timepoint (week 8, 16, 24 and 52), report the proportion of patients on fulfilling the "normal-level" criteria and summary statistics (mean, median, sd, 25%Q and 75%Q) of delta change, among patients not censored at each timepoint.

Secondary objective aa:

Report the proportion of patients that received extended induction

Secondary objective bb:

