P1 - l	Change in partial Mayo score	Δ-from baseline (mean ± sd)	Δ-from baseline (mean ± sd)	Δ-from baseline (mean ± sd)	Δ-from baseline (mean ± sd)
P1 - l	Change in full Mayo score	Δ-from baseline (mean ± sd)	Δ -from baseline (mean ± sd)	Δ-from baseline (mean ± sd)	Δ-from baseline (mean ± sd)
	Proportion of patients in sustained endoscopic remission (sub score = 0), mucosal healing (sub score 0-1) or endoscopic response (sub score				
P1 - m	reduction from baseline of ≥1) from week 8	-	n (%)	n (%)	n (%)

Objective	Outcome	Week 8	Week 16	week 24	week 52
P1 - n	Proportion of patients in physician assessed histological remission determined as inactive disease, or normal histology, and change from baseline in histology assessment (0= normal histology, 1= inactive disease and 2 = active disease)	n (%)	n (%)	n (%)	n (%)
P1 - o	Proportion of patients in sustained steroid free remission (pMayo and full Mayo score) (for all patients and for those treated with corticosteroids at baseline) and endoscopic remission (sub score = 0), mucosal healing (sub score 0-1) or endoscopic response (sub score reduction from baseline of ≥1) from week 8	-	n (%)	n (%)	n (%)
P1 - q	Proportion of patients with corticosteroid tapering	n (%)	n (%)	n (%)	n (%)
P1 - q	Corticosteroid tapering rates	mean ± sd	mean ± sd	mean ± sd	mean ± sd
P1 - q	Corticosteroid tapering doses	mean ± sd	mean ± sd	mean ± sd	mean ± sd
P1 - r	Proportion of patients with improvement in stool frequency sub score of 1 or more points and change from baseline in stool frequency sub score	n (%)	n (%)	n (%)	n (%)

Objective	Outcome	Week 8	Week 16	week 24	week 52
	Proportion of patients with improvement in				
P1 - s	rectal bleeding sub score of 1 or more points	n (%)	n (%)	n (%)	n (%)
		Δ-from baseline	Δ-from baseline	Δ-from baseline	Δ-from baseline
P1 - s	change from baseline in rectal bleeding sub score		(mean ± sd)	(mean ± sd)	(mean ± sd)
	Proportion of patients reaching normal P-CRP				
P1 - t	levels (below 4mg/L)	n (%)	n (%)	n (%)	n (%)
P1 - t	change from baseline in P-CRP levels	Δ-from baseline (mean ± sd)	Δ -from baseline (mean \pm sd)	Δ -from baseline (mean \pm sd)	Δ-from baseline (mean ± sd)
Ρ1-ι	Change Ironi baseline in F-CKF levels	(mean ± su)	(mean ± su)	(mean ± su)	(IIIeaii±Su)
	Proportion of patients reaching normal B-hb				
P1 - u	levels (men: 134–167 g/L, women: 117–155 g/L)	n (%)	n (%)	n (%)	n (%)
		Δ-from baseline	Δ-from baseline	Δ-from baseline	Δ-from baseline

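### Objective q divides corticosteroid tapering by all uncensored patients, so the reported proportion mixes corticosteroid use with tapering among users

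*SAP*

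**What the plan says.** Objective q (Protocol 7.3.1.q, repeated in SAP 2.2) reads "Proportion of patients with corticosteroid tapering at weeks 8/16/24/52 and their tapering rates and doses". The SAP adds a caution: "note after further discussions, the data required for objective q might not be present in the available medical records and/or prescriptions". The analysis is nevertheless kept in SAP 7.2, and Table 3 reserves three rows for it.

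SAP 7.2 builds the result in three steps:
- Classification: "For each patient, define the corticosteroid tapering as Yes/No based on the latest available data". There is no not-applicable category and no rule for what counts as a Yes.
- Proportion: "report the proportion of patients that had corticosteroid tapered, among patients not censored at each timepoint".
- Rates and doses: "report summary statistics (mean, median, sd, 25%Q and 75%Q) of tapering rates and doses among patients that had corticosteroids tapered".

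The plan restricts or splits the population for comparable endpoints. Objective h begins with "Select only patients with baseline f-calprotectin above 250 mg/kg at baseline". Objective d asks for results "for all patients and for those treated with corticosteroids at baseline", and objectives k and o do the same. Objective q does neither.

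Table 1 records concomitant corticosteroids and 5-ASA under one shared entry for product and dose. In Table 3, "Corticosteroid tapering doses" is a single row of mean ± sd, and tapering rates have another. Neither row names a unit, a product split or a conversion.

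**The concern.** Only a patient who has been taking a corticosteroid can taper it. With every uncensored patient in the denominator, a patient who never used one is recorded in the same way as a user whose dose was never reduced. The row then combines two quantities: how common corticosteroid use was, and how often users tapered.

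Protocol section 6 lists avoiding side effects of long-term corticosteroid use among the aims of UC treatment, so readers will probably take this row as a measure of steroid sparing. Read that way, it understates tapering among users by an amount they cannot see. It also cannot safely be compared with another cohort, or between timepoints, if the share of users differs.

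The dose and rate rows raise a smaller question of scale. If several corticosteroid products are recorded and pooled without a stated scale, the mean can change because the mix of products changes.

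**Working it through.** **Inputs.** The denominator rule comes from SAP 7.2, objective q. Study size is 100-150 (SAP 2.1). The documents give no corticosteroid-use share, no tapering share and no figure for q, so there is nothing to reproduce. Both shares below are assumptions shown as ranges.

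**Formula.** Let N be the patients not censored at a timepoint, s the share of them with a corticosteroid to taper, and t the share of those users who tapered.

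- Users: u = s × N. Tapered: x = t × u.
- Reported under SAP 7.2: x / N = s × t.
- Among users: x / u = t.

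**Results for N = 100.**

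| s (assumed) | t (assumed) | Users | Tapered | SAP row | Among users |
|---|---|---|---|---|---|
| 30% | 50% | 30 | 15 | 15% | 50% |
| 30% | 80% | 30 | 24 | 24% | 80% |
| 50% | 50% | 50 | 25 | 25% | 50% |
| 50% | 80% | 50 | 40 | 40% | 80% |
| 70% | 50% | 70 | 35 | 35% | 50% |
| 70% | 80% | 70 | 56 | 56% | 80% |

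The percentages at N = 150 are the same apart from rounding to whole patients.

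**The two parts cannot be separated.** 0.30 × 0.80 = 0.24 and 0.60 × 0.40 = 0.24. Both cohorts would show 24%, although tapering among users differs twofold.

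**Can a reader recover t from the shells?** That needs the number of users.
- Table 2 has no row for corticosteroid use at baseline.
- Table 4 counts prior corticosteroid treatment, which is not use at index.
- The Table 3 rows for d and k have no baseline-corticosteroid split.
- The Table 3 row for o mentions that group, but inside one combined remission and endoscopy row.

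No shell supplies u.

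**Precision.** The 95% Wilson interval has centre (p + z²/2n)/(1 + z²/n) and half-width z√(p(1−p)/n + z²/4n²)/(1 + z²/n), with z = 1.96. For s = 30% and t = 80%, 24/100 gives 16.7% to 33.2% and 24/30 gives 62.7% to 90.5%. The user-based interval is wider (27.8 against 16.5 points), but it describes tapering among users.

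**Dose and rate rows.** These are already limited to patients who tapered, so the denominator problem does not reach them. No size can be computed, because the documents name no product, unit or dose.

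**The case against.** The strongest defence is that the all-patient denominator follows the objective as worded, which asks for a proportion of patients and names no user group. Objectives d, k and o report all patients as well as baseline users, so an all-patient figure is a recognised quantity in this plan. That stands: the all-patient row answers the literal question and may be kept. It does not remove the need for a user-based row, because the shells leave readers unable to derive one.

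Second, the SAP itself doubts that the data for q will exist. That also stands as a warning about feasibility. The note does not withdraw q, however, and patchy data make an explicit N more useful.

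Third, limiting the denominator to index users leaves out patients who start a corticosteroid later and then taper. This is right, and the fix counts them separately.

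Fourth, the SAP does not define a Yes for tapering or the unit of a tapering rate. A new denominator does not cure that gap.

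A reader might also infer that doses will be averaged in raw milligrams and that the dose rows cannot be interpreted. The documents do not support this. They are silent on scale, and the product-and-dose entry is shared with 5-ASA, so it does not show that several corticosteroid products will be pooled.

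**Conclusion.** The point holds for the proportion row. As written, it estimates s × t. Under assumed use of 30-70% and assumed tapering of 50-80% among users, it would show 15-56% where the user-based figure is 50-80%. The dilution factor is s itself, which the documents do not give, so the true size is unknown. The formula also assumes that every patient without a corticosteroid is classified No, which follows from a Yes/No rule applied to each patient.

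Two stronger conclusions are tempting and should not be drawn. One is that the row mainly reflects baseline corticosteroid use: it depends on both factors, and nothing in the documents shows which dominates. The other is that objective q goes unanswered: the all-patient proportion meets its literal wording.

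The dose and rate rows are a secondary matter of missing detail, and scale matters only if more than one corticosteroid product is recorded. Severity is minor: q is one of 29 lettered items (a to cc) under the effectiveness objective, all descriptive, and no hypothesis or decision rests on it.

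**What to change.** In SAP 7.2, objective q, and in Table 3:

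1. Report the tapering proportion among patients with a corticosteroid recorded at index and not censored at the timepoint, with n/N in each cell.
2. Keep the all-patient proportion as a second, labelled row if wanted.
3. Count patients who start a corticosteroid after index separately, with their own n/N.
4. State the unit for tapering doses and rates. If more than one corticosteroid product is recorded, summarise by product or on one stated equivalent scale.
5. In the same edit, state what qualifies as a Yes for tapering, since every row depends on it.

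The cost is SAP text and a few table rows. Product and dose are already planned variables in Table 1, so no new variable is needed to identify index users, provided the records contain the data, which the SAP's own note leaves open. The downside is smaller cells. Protocol 8.6 does not allow groups of fewer than 5 patients to be exported. With 15 tapered patients (s = 30%, t = 50%, N = 100), a split over four products would average 15/4 = 3.75 each, so a single stated scale may be the more workable option for the dose rows.

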#### 7.1. Definitions

Active disease:

• An endoscopic Mayo sub-score  $^{12}$  of  $\geq 2$  or fecal-calprotectin (f-calpro)  $\geq 250$  mg/kg.

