#### 8.2.1. Inclusion Criteria

Patients must meet all of the following inclusion criteria to be eligible for inclusion in the study:

- 1. Xeljanz (tofacitinib) usage for ulcerative colitis.
- 2. Diagnosis of ulcerative colitis (ICD-10: K51.0, K51.1, K51.2, K51.3, K51.5, K51.8, K51.9) between January 2010 and December 2021 (incident or prevalent).

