Fecal calprotectin	Primary objective 7.2.1.d, Secondary objectives 7.3.1.g and 7.3.1.h.	mg/kg
Plasma CRP	Primary objective 7.2.1.d Secondary objective 7.3.1.t	mg/L
Blood hemoglobin	Primary objective 7.2.1.d, Secondary objective 7.3.1.u	g/L
Blood leukocytes	Primary objective 7.2.1.d Secondary objective 7.3.1.v	cells/L
Blood thrombocytes	Primary objective 7.2.1.d Secondary objective 7.3.1.w	cells/L
Blood lymphocytes	Primary objective 7.2.1.d Secondary objective 7.3.1.x	cells/L
Blood neutrophiles	Primary objective 7.2.1.d Secondary objective 7.3.1.y	cells/L
Plasma albumin	Primary objective 7.2.1.d Secondary objective 7.3.1.z	g/L
Tofacitinib dose	Secondary objectives 7.3.1.a, 7.3.1.aa and 7.3.1.bb	mg*times/per day or "not on treatment"
Colectomies	Secondary objective 7.3.1.cc	Date
Type of healthcare contact	Secondary objective 7.3.1.cc	outpatient visit, remote contact, emergency visit or hospitalization

Variable	Role	Operational definition
Prior IBD treatments	Secondary objective 7.3.2	Yes/no (For each treatment)
 corticosteroids 5-aminosalicylic acid (5-ASA) azathioprine 6-mercaptopurine methotrexate cyclosporine ustekinumab vedolizumab adalimumab infliximab golimumab 		
Concomitant medications o corticosteroids o 5-ASA	Secondary objective 7.3.1.q,	product & dose
Extraintestinal manifestations: arthralgia, arthritis, sacroiliitis, pyoderma gangrenosum, erythema nodosum, primary sclerosing cholangitis, uveitis, ankylosing spondylitis, aphthous stomatitis, psoriasis	CCI	Yes/no per pre-specified list
Prior diagnoses	CCI	Yes/no per pre-specified list
Death date or lost to follow up	Used to define end of follow up	Date

Further operational definitions from the collected data include:

Active disease:

• An endoscopic Mayo sub-score of ≥ 2 or fecal-calprotectin (f-calpro) > 250 mg/kg.

Clinical response:

• A full Mayo score decrease of ≥ 3 points and a decrease of $\geq 30\%$ from baseline, with a decrease of ≥ 1 point on the rectal bleeding subscore or an absolute rectal bleeding score of ≤ 1 .

• A partial Mayo score (ie, Mayo score without endoscopic assessment) decrease of ≥2 points and reduction of at least 25% in partial Mayo (pMayo) score from baseline with an accompanying decrease in rectal bleeding sub score of ≥1 point or absolute rectal bleeding sub score of ≤1.

Clinical remission:

- A full Mayo score of ≤ 2 points with no individual sub score exceeding 1 point, with rectal bleeding sub-score of 0.

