4 ANALYSIS SETS/POPULATIONS

4.1 FULL ANALYSIS SET

Full analysis set includes all patients fulfilling inclusion criteria, and not excluded due to exclusion criteria.

- 1. Xeljanz® (tofacitinib) usage for ulcerative colitis.
- 2. Diagnosis of ulcerative colitis (ICD-10: K51.0, K51.1, K51.2, K51.3, K51.5, K51.8, K51.9) between January 2010 and December 2021 (incident or prevalent).

Patients will be excluded if:

- 1. Age <18 years at the start of tofacitinib use.
- 2. Use of tofacitinib before reimbursement (01 Mar 2019).
- 3. < 8 weeks of treatment with to facitinib at the start of data mining.
- 4. History of panproctocolectomy, IPAA or ileostomy.

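### Clinical response and sub-score improvement are scored in all non-censored patients, including any whose baseline score is too low to meet the criterion

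*SAP*

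**What the plan says.** **Entry.** The first inclusion criterion (Protocol 8.2.1) is "Xeljanz (tofacitinib) usage for ulcerative colitis". The second is a K51 diagnosis between January 2010 and December 2021. The exclusions (Protocol 8.2.2) concern age, use before reimbursement, under 8 weeks of treatment and previous bowel surgery. None sets a Mayo, endoscopic or f-calpro minimum. SAP 4.1 adds no restriction: "Full analysis set includes all patients fulfilling inclusion criteria, and not excluded due to exclusion criteria". The Subgroups heading (SAP 4.4) has no visible text.

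**Criteria.** Full-Mayo response (SAP 2.1) begins "A full Mayo score decrease of ≥ 3 points and a decrease of" at least 30%. Partial-Mayo response needs a fall of at least 2 points and at least 25%. Both add a rectal bleeding condition. Objectives r and s need a fall of at least 1 point in the sub-score.

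**Who is scored.** For r and s, SAP 7.2 says "For each patient, define the fulfilment of the improvement criteria as Yes/No based on the latest available data" and reports among patients not censored at the timepoint. Objectives b, c, d, e, g and n follow the same pattern, and p repeats b and c by colonic extent. Objective f follows every patient from index to response, discontinuation or end of data collection. Objective h, by contrast, restricts on baseline: "Select only patients with baseline f-calprotectin above 250 mg/kg at baseline".

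**Active disease.** Protocol 7.1 defines it as "An endoscopic Mayo sub-score" of 2 or more, or f-calpro at or above 250 mg/kg. SAP 2.1 has "An endoscopic Mayo sub-score of ≥ 2 or fecal-calprotectin (f-calpro) > 250 mg/kg".

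**Tables.** SAP Table 3 has one row for the number of patients per timepoint. SAP Table 2 summarises the Mayo score by mean and median, with no row for partial Mayo, stool frequency or rectal bleeding.

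**The concern.** A criterion based on a fall in a score can be met only by patients whose score has room to fall. With no activity minimum at entry, some patients may start with few or no symptoms. Objective d, for example, expects some to be on corticosteroids at baseline, which may already have controlled symptoms. Under SAP 7.2 such patients count as non-responders at every timepoint for c, e, r and s. In f they can only discontinue or be censored.

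Three things are at stake. The reported response would mix treatment outcome with baseline case mix. The strata in p could differ because their baselines differ. And the tables could look inconsistent: a patient with partial Mayo 0 at baseline and at week 8 is a success for remission (b) and a failure for response (c).

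**Working it through.** The plan states no sample size, power or expected rate (Protocol 8.5), so there is no figure to reproduce.

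**Inputs from the documents:** each Mayo sub-score runs 0–3 (Table 1); response and remission definitions (SAP 2.1); denominators (SAP 7.2); expected N of 100–150 (Protocol 8.5). **Not in the documents, so assumed:** q, the share of scored patients whose baseline is too low; p, the response proportion among the others.

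**1. Which baselines make the criterion impossible.** A score cannot fall below 0, so a fall of d points needs a baseline of at least d. From any baseline at or above d, reaching 0 is a 100% fall with rectal bleeding 0, so the percentage and bleeding conditions exclude no further baselines. Of the 4⁴ = 256 sub-score combinations:
- Full-Mayo response is impossible for totals 0–2: 1 + 4 + 10 = 15 combinations.
- Partial-Mayo response is impossible for partial totals 0–1: (1 + 3) × 4 endoscopic values = 16 combinations.
- Improvement in r or s is impossible whenever that sub-score is 0.

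These count score patterns, not patients, and say nothing about q.

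**2. Effect on a proportion.** Reported = [p(1−q)N + 0·qN]/N = p(1−q). The shortfall is pq.

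| p | q = 0 | q = 10% | q = 20% | q = 30% |
|---|---|---|---|---|
| 40% | 40% | 36% | 32% | 28% |
| 50% | 50% | 45% | 40% | 35% |
| 60% | 60% | 54% | 48% | 42% |

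Over p = 40–70% and q = 5–40% the shortfall runs from 0.40 × 0.05 = 2 points to 0.70 × 0.40 = 28 points. For scale, the 95% half-width at 50% is 1.96 × √(0.25/100) = 9.8 points with N = 100, and 8.0 points with N = 150.

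**3. Time to response.** Patients unable to respond contribute no response events, so the cumulative incidence in the whole cohort is (1−q) times that in patients able to respond.

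**4. Strata in p.** With p = 60% in two strata, q = 10% in one and 30% in the other gives 54% against 42%, a 12-point gap with no difference among patients able to respond. With equal p and equal q there is no gap.

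**5. Remission (b, d).** These are absolute states. Seven combinations already meet full-Mayo remission at baseline and 12 meet partial-Mayo remission. If 20% start in remission, 80% of them remain there and 50% of the rest reach it (all assumed), the report is 0.20 × 0.80 + 0.80 × 0.50 = 56%, against 50% in those not in remission at baseline.

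**6. Would an Active disease restriction cure it?** Of the 2 × 64 = 128 combinations with endoscopic sub-score 2–3:
- 32 have rectal bleeding 0 and 32 have stool frequency 0;
- 8 have partial Mayo below 2 and 1 has full Mayo below 3;
- 2 × 3 = 6 already meet partial-Mayo remission.

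Patients active by f-calpro alone can have any Mayo value. The restriction would not do the job.

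**The case against.** The best defence is that the study is descriptive, with no hypotheses. The proportion of all treated patients who respond is a legitimate summary. Nothing in the documents shows that any patient starts below the thresholds. Baseline Mayo and f-calpro are tabulated, and change from baseline accompanies l, r and s. The primary objective is untouched. Much of this stands: it makes the effect conditional and limits its importance. It does not answer the point about the tables. A mean and median full Mayo score do not show how many patients had partial Mayo 0–1 or a sub-score of 0, and only aggregate results leave the Findata environment (Protocol 8.6), so a reader could not recover the denominators.

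A reader might also infer more than the documents support:
- **That b, d and g are depressed too.** b and d are absolute states, which patients already in remission can raise. g is a relative fall, arithmetically possible from any baseline above 0.
- **That h is the only restricted endpoint.** Objectives i, j, k, m and o also select patients, by remission at the timepoints. h is the only one that selects on a raised baseline value.
- **That Active disease is never used.** It is not used in the visible text, but some objectives and two Table 1 roles are blacked out.

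**Conclusion.** The point holds for c, e, f, r, s and the response part of p. SAP 7.2 keeps in the denominator or risk set any patient whose baseline rules out the criterion, and this lowers the reported figure relative to patients able to respond by pq. At assumed p = 60% and q = 10–30% that is 6 to 18 points; at q = 0 it is nothing.

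It would be tempting to say that the plan understates response and that the strata in p are not comparable. Neither is established. The documents do not give q. Carry-forward of the latest value, the exclusion for under 8 weeks of treatment and the non-censored denominators also move these estimates, so the net direction is unknown. The strata are distorted by this mechanism only if q differs between them.

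The endpoints are secondary and descriptive, so this is a change that should be made rather than one on which the study depends.

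**What to change.** In SAP 7.2 and Table 3:
- For c, e, f and the response part of p, use patients with baseline partial Mayo ≥2 (partial rows) or full Mayo ≥3 (full rows).
- For r and s, use patients with a baseline of at least 1 on that sub-score.
- State the eligible N in each row, subject to the rule that groups under 5 cannot be exported (Protocol 8.6). Keep the all-patient figure alongside if wanted.
- Leave g as defined. The protocol restricts h on baseline f-calpro and does not restrict g.
- Report b and d additionally in patients not in remission at baseline.
- If Active disease is to be used anywhere, reconcile the two f-calpro limits (at or above 250 in Protocol 7.1, above 250 in SAP 2.1).

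The cost is SAP wording and table rows, from baseline values already collected. Denominators become somewhat smaller. Where few patients are ineligible, showing both the eligible and the all-patient N could reveal a group under 5 by subtraction, so some cells may have to be suppressed.
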